General guidance for dose modifications and treatment delays and discontinuation	
• The dose of cobimetinib and vemurafenib can be reduced by one dose level in the run-in period (see Section 5.1.5.1).• There will be no dose modifications for atezolizumab.• During the triplet combination period, Cycle 1 and beyond, the dose of cobimetinib can be reduced by 20 mg (one dose level) up to two times (i.e., from 60 mg to 40 mg and then from 40 mg to 20 mg). If further dose reduction is indicated after two dose reductions, the patient must discontinue cobimetinib but may continue treatment with atezolizumab and/or vemurafenib at the investigator's discretion.• During the triplet combination period, in order to preserve the blind, two reductions in tablet number will be allowed in both Arm A and Arm B. The first dose reduction will be from 3 tablets in the large bottle plus 1 tablet in the small bottle BID to 2 tablets in the large bottle plus 1 tablet in the small bottle BID; this will represent a true dose reduction in Arm A (from 960 mg BID to 720 mg BID) and in Arm B (from 720 mg BID to 480 mg BID). If a second dose reduction is required, patients in both arms will reduce from 2 tablets in the large bottle plus 1 tablet in the small bottle BID to 2 tablets in the large bottle BID. This will represent a true dose reduction in Arm A (from 720 mg BID to 480 mg BID) whereas in Arm B, because the small bottle contains placebo tablets, it will represent a "false" dose reduction (with dosing maintained at 480 mg BID). If further dose reduction is indicated after two dose reductions, the patient must discontinue vemurafenib but may continue treatment with atezolizumab and/or cobimetinib at the investigator's discretion.• If atezolizumab is withheld and corticosteroids are initiated for treatment of a toxicity, corticosteroids must be tapered over ≥ 1 month to ≤ 10 mg/day oral prednisone or equivalent before atezolizumab can be resumed. If atezolizumab is withheld for > 12 weeks, the patient should be discontinued from atezolizumab. Study treatment may be withheld for > 12 weeks to allow for patients to taper off corticosteroids prior to resuming treatment. Atezolizumab can be resumed after being withheld for > 12 weeks for patients experiencing clinical benefit as determined by the investigator. The Medical Monitor is available to advise as need.• If either cobimetinib or vemurafenib is withheld for > 28 days because of toxicity, the patient should be discontinued from that drug, unless resumption of treatment is approved by the investigator. The Medical Monitor is available to advise as needed.• After dose reduction, consideration may be given to allow for dose escalation of cobimetinib or vemurafenib by a maximum of one dose level following resolution of the adverse event that resulted in dose modification, provided there are no safety concerns (see Section 5.1.5.2). Escalation is not permitted during the run-in period (see Section 5.1.5.1).

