Abdominal pain in combination with blood or mucus in stool and/or Grade ≥ 3 diarrhea with possible colitis (e.g., peritoneal signs, ileus, or fever)	
 Withhold all study treatment. Discontinue medications that may exacerbate colitis (e.g., NSAIDS). Initiate maximum supportive care and monitor patient closely. Investigate etiology, ruling out bowel perforation. Refer patient to GI specialist. If immune-mediated colitis is suspected, consider treatment with 1–2 mg/kg/day IV methylprednisolone or equivalent and convert to 1–2 mg/kg/day oral prednisone or equivalent upon improvement. Consider TNF antagonists for refractory diarrhea. If event resolves to Grade 1 or better within 12 weeks, resume atezolizumab at fixed dose. If not, permanently discontinue atezolizumab.^{a,b,c} If event resolves to Grade 1 or better within 28 days, resume cobimetinib and vemurafenib with doses reduced by one level. If not, permanently discontinue cobimetinib and vemurafenib. When study treatment is resumed, administer supportive care and/or prophylactic treatment.

CRP = C-reactive protein; GI = gastrointestinal; IV = intravenous; NSAID = non-steroidal anti-inflammatory drug; TNF = tumor necrosis factor.

- ^a If corticosteroids have been initiated, they must be tapered over ≥ 1 month to ≤ 10 mg/day oral prednisone or equivalent before atezolizumab can be resumed.
- ^b Atezolizumab may be withheld for a period of time beyond 12 weeks to allow for corticosteroids to be reduced to ≤ 10 mg/day oral prednisone or equivalent. The acceptable length of the extended period of time must be based on an assessment of the benefits and risks by the investigator and in alignment with the protocol requirements for the duration of treatment and documented by the investigator. The Medical Monitor is available to advise as needed.
- ^c Resumption of atezolizumab may be considered in patients who are deriving benefit and have fully recovered from the immune-mediated event. The decision to re-challenge patients with atezolizumab should be based on *the* investigator's benefit–risk *assessment* and documented by the investigator (or an appropriate delegate). The Medical Monitor is available to advise as needed.

Table 3 Guidelines for Management of Patients Who Experience Specific Adverse Events (cont.)

Event	Action to Be Taken
Gastrointestinal toxicity (cont.)	

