Diarrhea and colitis, Grade 4	
 Permanently discontinue all study treatment and contact Medical Monitor.^c Discontinue medications that may exacerbate colitis (e.g., NSAIDS) while investigating etiology. Initiate maximum supportive care and monitor patient closely. Investigate etiology, referring patient to GI specialist for evaluation of possible colitis, including biopsy if appropriate. Initiate treatment with 1–2 mg/kg/day IV methylprednisolone or equivalent and convert to 1–2 mg/kg/day oral prednisone or equivalent upon improvement. If event does not improve within 48 hours after initiating corticosteroids, consider adding an immunosuppressive agent. If event resolves to Grade 1 or better, taper corticosteroids over ≥ 1 month.

GI=gastrointestinal; IV=intravenous; NSAID=non-steroidal anti-inflammatory drug.

- ^a If corticosteroids have been initiated, they must be tapered over ≥ 1 month to ≤ 10 mg/day oral prednisone or equivalent before atezolizumab can be resumed.
- ^b Atezolizumab may be withheld for a period of time beyond 12 weeks to allow for corticosteroids to be reduced to ≤ 10 mg/day oral prednisone or equivalent. The acceptable length of the extended period of time must be based on *the investigator's benefit-risk assessment* and in alignment with the protocol requirements for the duration of treatment and documented by the investigator. The Medical Monitor is available to advise as needed.
- ^c Resumption of atezolizumab may be considered in patients who are deriving benefit and have fully recovered from the immune-mediated event. The decision to re-challenge patients with atezolizumab should be based on *the investigator's benefit-risk assessment* and documented by the investigator. The Medical Monitor is available to advise as needed.

Table 3 Guidelines for Management of Patients Who Experience Specific Adverse Events (cont.)

Event	Action to Be Taken
New skin lesion	
Cutaneous primary malignancy or skin lesion suggestive of cutaneous primary malignancy	
Continue all study treatment.Treat per institutional guidelines.
Dermatologic toxicity	
General guidance	
A dermatologist should evaluate persistent and/or severe rash or pruritus. A biopsy should be considered unless contraindicated.
Photosensitivity, Grade 1	
Continue all study treatment.Initiate supportive care.

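### Protocol Table 3 gives opposite cobimetinib and vemurafenib instructions for Grade 4 diarrhea with possible colitis that resolves within 28 days

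*Protocol*

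**What the plan says.** The gastrointestinal part of Table 3 (Protocol Section 5.1.5.4) has one row defined by presentation, followed by rows defined by grade.

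- **Presentation row.** It covers abdominal pain with blood or mucus in the stool and/or "Grade ≥ 3 diarrhea with possible colitis (e.g., peritoneal signs, ileus, or fever"). All study treatment is withheld. The work-up includes "Investigate etiology, ruling out bowel perforation". For the two oral drugs the rule is "If event resolves to Grade 1 or better within 28 days, resume cobimetinib and vemurafenib with doses reduced by one level"; without recovery in that time, both stop for good. Atezolizumab is resumed if the event recovers within 12 weeks.
- **Grade 4 row (diarrhea and colitis).** "Permanently discontinue all study treatment and contact Medical Monitor". The attached footnote c softens this for one drug: "Resumption of atezolizumab may be considered in patients who are deriving benefit and have fully recovered from the immune-mediated event". It does not mention cobimetinib or vemurafenib.

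Section 4.6.2 makes permanent discontinuation mandatory for any adverse event for which the Section 5.1 guidelines require it.

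**The concern.** Neither row excludes the other. The presentation row starts at Grade 3 and has no ceiling. The Grade 4 row makes no exception for unconfirmed colitis; it orders a specialist evaluation for that possibility. The same patient can therefore fall under both rows, and they disagree on whether cobimetinib and vemurafenib may ever be given again.

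This is a safety instruction for a Grade 4 event, and Section 1.5.3 lists gastrointestinal toxicity among the overlapping toxicities of the three drugs. A site that restarts under the presentation row contravenes the Grade 4 row, which Section 4.6.2 appears to make binding. A site that stops under the Grade 4 row omits a restart that the presentation row directs. A monitor cannot tell from the text whether a restart is directed care or a protocol deviation.

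**Working it through.** The plan states no figure on this point, so the check compares the texts and applies the protocol's dose steps.

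**1. Do the rows overlap?** The presentation row's heading can be read in two ways: abdominal pain is required only with blood or mucus in the stool, or it is required for every trigger. Take a patient with Grade 4 diarrhea, abdominal pain and fever or peritoneal signs. That patient meets the presentation row on either reading. The patient also meets the Grade 4 row, which cannot be limited to confirmed colitis because it asks for colitis to be evaluated.

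**2. What does each applicable row direct on recovery to Grade 1 or better within 28 days?**

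| Grade | Presentation row: cobimetinib and vemurafenib | Grade-specific row: cobimetinib and vemurafenib | Agree? |
|---|---|---|---|
| 3 | Resume one level lower | Resume one level lower | Yes |
| 4 | Resume one level lower | Stop permanently | No |

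The conflict is confined to Grade 4.

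**3. Dose consequence.** One level is 20 mg QD for cobimetinib and 240 mg BID for vemurafenib (Section 5.1.5.2). For vemurafenib, the Table 3 general guidance describes the first tablet reduction as follows: "this will represent a true dose reduction in Arm A (from 960 mg BID to 720 mg BID) and in Arm B" (there from 720 mg to 480 mg BID). From starting triple-combination doses:

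- Cobimetinib: 60 − 20 = 40 mg QD, against 0 mg under the Grade 4 row.
- Vemurafenib, Arm A: 960 − 240 = 720 mg BID, against 0 mg.
- Vemurafenib, Arm B: 720 − 240 = 480 mg BID, against 0 mg.

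**4. Where the conflict does not arise or is not claimed.**

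- For a drug already reduced twice, both rows end in discontinuation. For cobimetinib the general guidance says "If further dose reduction is indicated after two dose reductions, the patient must discontinue cobimetinib", and it has the same rule for vemurafenib.
- During the run-in, Section 5.1.5.1 allows only one reduction, so a drug already reduced once cannot be restarted a level lower in that period.
- For recovery after day 28, nothing is claimed. The general guidance stops a drug withheld longer than 28 days for toxicity "unless resumption of treatment is approved by the investigator", and Section 5.1.5.3 has a similar exception involving the Medical Monitor.

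**5. Does any text rank the rows?**

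- Footnote c reopens atezolizumab only.
- The Section 5.1.5.4 introduction leaves room for clinical judgment but sets no order.
- The Table 3 general guidance sets dose steps and holding limits, not precedence.
- The Appendix 10 default for Grade 4 events concerns atezolizumab only, and its gastrointestinal entry refers back to Section 5.1.5.4.
- Elsewhere Table 3 does state when one row gives way to another. Its residual row is limited to toxicities not covered earlier, Grade 1 hyperthyroidism with TSH below 0.1 mU/L is sent to the Grade 2 row, and Grade 1 cranial nerve disorders are handled under the Grade 2 neuropathy guidance. The presentation row has no such link.

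**The case against.** The strongest reply is that Section 4.6.2 already settles the matter. If any applicable guideline requires permanent discontinuation, the patient must stop, and nothing makes a restart compulsory in the same way. The row naming Grade 4 is also the more specific and the more cautious one, it acts before the conditional restart could arise, and it requires contact with the Medical Monitor. On this view the presentation row only adds diagnostic work-up, and a cross-reference at the next amendment is enough.

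Part of this stands. Section 4.6.2 favors stopping, and the two possible errors are not equally serious: declining a restart after a Grade 4 event is easy to defend given the latitude for clinical judgment.

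It does not remove the conflict. Section 4.6.2 refers back to the Section 5.1 guidelines without saying which row governs. Nor can a site infer that Grade 4 always means stopping the oral drugs. Table 3 allows one or both to be restarted after Grade 4 photosensitivity, pulmonary events, pancreatitis, CPK elevation and events in the residual row, while Grade 4 dermatologic events stop all study treatment. A restart under the presentation row would not look out of place.

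Two smaller points are fair. The change needs amendment approval, and at Grade 4 the rows also differ on corticosteroids: to be considered if immune-mediated colitis is suspected in one, to be started in the other. Neither affects the conflict over the two oral drugs.

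**Conclusion.** The concern holds. For a Grade 4 event with abdominal pain and possible colitis that recovers to Grade 1 or better within 28 days, Table 3 directs both a reduced-dose restart and a permanent stop of cobimetinib and vemurafenib. That is two of three study drugs, at one grade and within one recovery window.

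The conclusion rests on reading the Grade 4 row as including suspected colitis, which its own work-up instruction supports. It does not depend on which reading of the abdominal pain wording is taken. The documents give no rate for such events, so the number of patients affected is unknown, and no effect on the PFS comparison is claimed. This is a conflicting safety rule rather than a missing detail, and it should be corrected.

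**What to change.** Add two sentences to the presentation row:

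> *For Grade 4 diarrhea or colitis, permanently discontinue study treatment per the Grade 4 row; the resumption rules in this row do not apply. The diagnostic and supportive steps in this row (including ruling out bowel perforation) still apply.*

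This takes the cautious direction that Section 4.6.2 supports. Cutting the heading back to Grade 3 would be worse, because the perforation check appears in the presentation row and not in the Grade 4 row, so the most severely ill patients would lose it. The heading, the corticosteroid and TNF-antagonist wording and footnotes a to c can stay as they are. The route back to atezolizumab through footnote c is then preserved. The difference in corticosteroid wording at Grade 4 would remain and could be tidied separately.

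The cost is two sentences in one table row and a memo to sites, with no change to data collection or analysis. Because this alters a treatment instruction, Section 9.6 calls for IRB/EC approval, and regulatory approval where locally required, before it takes effect, unless the immediate-hazard exception applies.

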5.1.3.7 Hypersensitivity and Severe Cutaneous Reactions

Serious hypersensitivity reactions, including anaphylaxis, have been reported in association with vemurafenib and upon re-initiation of treatment. Severe hypersensitivity reactions included generalized rash and erythema or hypotension. Drug reaction with eosinophilia and systemic symptoms has been reported in association with vemurafenib in the postmarketing setting. Severe dermatologic reactions have been reported in patients receiving vemurafenib, including cases of Stevens-Johnson syndrome and toxic epidermal necrolysis.

Guidelines for management of patients who develop hypersensitivity reactions and dermatologic events are provided in Section 5.1.5.3 (see [Table 3](#)).

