
BID=twice daily.

- ^a If corticosteroids have been initiated, they must be tapered over \geq 1 month to \leq 10 mg/day oral prednisone or equivalent before atezolizumab can be resumed.
- ^b Atezolizumab may be withheld for a longer period of time (i.e., $>$ 12 weeks after event onset) to allow for corticosteroids (if initiated) to be reduced to the equivalent of \leq 10 mg/day oral prednisone. The acceptable length of the extended period of time must be based on *the investigator's benefit–risk assessment* and in alignment with the protocol requirements for the duration of treatment and documented by the investigator. The Medical Monitor is available to advise as needed.
- ^c Resumption of atezolizumab may be considered in patients who are deriving benefit and have fully recovered from the immune-mediated event. The decision to re-challenge patients with atezolizumab should be based on *the investigator's benefit–risk assessment* and documented by the investigator. The Medical Monitor is available to advise as needed.

Table 3 Guidelines for Management of Patients Who Experience Specific Adverse Events (cont.)

Event	Action to Be Taken
IRRs, anaphylaxis, and hypersensitivity reaction	
 Guidelines for management of IRRs are provided in Appendix 10. For anaphylaxis precautions, see Appendix 6. For severe hypersensitivity reactions, permanently discontinue all study treatment.
Gastrointestinal toxicity	
Gastrointestinal events: general guidance	
 All events of diarrhea or colitis should be thoroughly evaluated for other more common etiologies. For events of significant duration or magnitude or associated with signs of systemic inflammation or acute phase reactants (e.g., increased CRP, platelet count, or bandemia): Perform sigmoidoscopy (or colonoscopy, if appropriate) with colonic biopsy, with three to five specimens for standard paraffin block to check for inflammation and lymphocytic infiltrates to confirm colitis diagnosis.

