Dermatologic event, Grade 2	
• Continue all study treatment.• Consider patient referral to dermatologist for evaluation and, if indicated, biopsy.• Initiate maximum supportive care (e.g., antihistamines, topical corticosteroids). If event does not improve, consider treatment with higher-potency topical corticosteroids.• If unresponsive to topical corticosteroids, consider oral prednisone 0.5 mg/kg/day.
Dermatologic event, Grade 3	
• Refer patient to dermatologist. A biopsy should be performed if appropriate, and, if possible, photographs of the rash should be obtained and submitted to the Sponsor. 
Acneiform rash:
 
• Withhold atezolizumab and cobimetinib. Continue vemurafenib.• Refer patient to dermatologist for evaluation and, if indicated, biopsy.• If event does not improve within 48–72 hours, consider treatment with 10 mg/day oral prednisone or equivalent, increasing dose to 1–2 mg/kg/day if event still does not improve.• If event resolves to Grade 2 or better within 12 weeks, resume atezolizumab at fixed dose. If not, permanently discontinue atezolizumab. ^{a,b,c}• If event resolves to Grade 2 or better within 28 days, resume cobimetinib with dose reduced by one level. If not, permanently discontinue cobimetinib.• When study treatment is resumed, consider treatment with topical corticosteroids and oral antibiotics. 
Non-acneiform (e.g., maculo-papular) rash:
 
• Withhold vemurafenib. Continue atezolizumab and cobimetinib.• If event resolves to Grade 2 or better within 28 days, resume vemurafenib with dose reduced by one level. If not, permanently discontinue vemurafenib.

- ^a If corticosteroids have been initiated, they must be tapered over \geq 1 month to \leq 10 mg/day oral prednisone or equivalent before atezolizumab can be resumed.
- ^b Atezolizumab may be withheld for a period of time beyond 12 weeks to allow for corticosteroids to be reduced to \leq 10 mg/day oral prednisone or equivalent. The acceptable length of the extended period of time must be based on *the investigator's benefit–risk assessment* and in alignment with the protocol requirements for the duration of treatment and documented by the investigator. The Medical Monitor is available to advise as needed.

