- ^c Resumption of atezolizumab may be considered in patients who are deriving benefit and have fully recovered from the immune-mediated event. The decision to re-challenge patients with atezolizumab should be based on *the investigator's benefit–risk assessment* and documented by the investigator. The Medical Monitor is available to advise as needed.

Table 3 Guidelines for Management of Patients Who Experience Specific Adverse Events (cont.)

Event	Action to Be Taken
Dermatologic toxicity (cont.)	
Dermatologic event, Grade 4	
Permanently discontinue all study treatment and contact Medical Monitor.^c
Stevens-Johnson syndrome or toxic epidermal necrolysis (any grade)	
Additional guidance for Stevens-Johnson syndrome or toxic epidermal necrolysis:
 
Withhold atezolizumab for suspected Stevens-Johnson syndrome or toxic epidermal necrolysis.Confirm diagnosis by referring patient to a specialist (dermatologist, ophthalmologist, or urologist as relevant) for evaluation and, if indicated, biopsy.Follow the applicable treatment and management guidelines above.If Stevens-Johnson syndrome or toxic epidermal necrolysis is confirmed, permanently discontinue atezolizumab.

^a If corticosteroids have been initiated, they must be tapered over \geq 1 month to \leq 10 mg/day oral prednisone or equivalent before atezolizumab can be resumed.

^b Atezolizumab may be withheld for a period of time beyond 12 weeks to allow for corticosteroids to be reduced to \leq 10 mg/day oral prednisone or equivalent. The acceptable length of the extended period of time must be based on *the investigator's benefit-risk assessment* by the investigator and in alignment with the protocol requirements for the duration of treatment and documented by the investigator. The Medical Monitor is available to advise as needed.

^c Resumption of atezolizumab may be considered in patients who are deriving benefit and have fully recovered from the immune-mediated event. The decision to re-challenge patients with atezolizumab should be based on *the investigator's benefit-risk assessment* and documented by the investigator. The Medical Monitor is available to advise as needed.

Table 3 Guidelines for Management of Patients Who Experience Specific Adverse Events (cont.)

Elevations in ALT, AST, and/or bilirubin during run-in period	

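### Table 3's row for Stevens-Johnson syndrome and toxic epidermal necrolysis names only atezolizumab, so a confirmed Grade 3 case handled under the non-acneiform rash guidance can resume vemurafenib

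*Protocol*

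**What the plan says.** The SJS/TEN row closes the dermatologic block of Table 3 (Protocol 5.1.5.4) and is marked as additional guidance. It withholds atezolizumab on suspicion, asks for specialist confirmation, and then says: "Follow the applicable treatment and management guidelines above". It ends with "If Stevens-Johnson syndrome or toxic epidermal necrolysis is confirmed, permanently discontinue atezolizumab". It gives no action for vemurafenib or cobimetinib.

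The rows above it are graded:

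- Grades 1 and 2: all study treatment continues.
- Grade 3, acneiform rash: "Withhold atezolizumab and cobimetinib. Continue vemurafenib".
- Grade 3, non-acneiform rash (maculo-papular is the example given): vemurafenib is withheld while the other two drugs continue. Then: "If event resolves to Grade 2 or better within 28 days, resume vemurafenib with dose reduced by one level". If the event does not reach that grade in time, vemurafenib is permanently stopped.
- Grade 4: "Permanently discontinue all study treatment and contact Medical Monitor".

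Section 5.1.3 lists hypersensitivity and severe cutaneous reactions among the identified risks of vemurafenib. Section 5.1.3.7 adds: "Severe dermatologic reactions have been reported in patients receiving vemurafenib, including cases of Stevens-Johnson syndrome and toxic epidermal necrolysis". It sends the reader to Table 3 for management.

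**The concern.** Section 5.1.3.7 leaves management to Table 3, so Table 3 is where a vemurafenib rule for SJS/TEN should stand. The row written for that diagnosis does not contain one. It passes the decision to rows written for rash in general, and the only Grade 3 branch there that withholds vemurafenib also provides for resuming it.

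What is at stake is re-exposure of a patient with a confirmed severe cutaneous reaction to a drug the protocol itself links to that reaction. Avoiding this depends on the investigator choosing a different rule over the row that names the diagnosis.

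**Working it through.** No arithmetic applies. The check is to follow a confirmed case through the rules.

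**Confirmed Grade 3 case, read from the SJS/TEN row**

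1. Atezolizumab is permanently discontinued. The non-acneiform row says to continue it, but the SJS/TEN row is more specific and reasonably prevails.
2. For the other drugs the reader is sent to the graded rows. Grade 3 has two branches. Acneiform rash keeps vemurafenib going, which leaves non-acneiform as the closer fit.
3. Under that branch vemurafenib is withheld immediately, in either arm and in either treatment period.
4. If the event is Grade 2 or better within 28 days, vemurafenib restarts one dose level lower. Otherwise it is permanently stopped.
5. Cobimetinib continues throughout.

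**Other grades.** At Grade 4 all treatment stops, so there is no gap. Grades 1 and 2, read literally, continue vemurafenib, but the documents do not show whether SJS/TEN can be graded that low. Nothing here rests on those rows.

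**Other rules that could stop vemurafenib**

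| Place in protocol | What it does | Why it does not close the gap |
|---|---|---|
| Table 3, hypersensitivity row | "For severe hypersensitivity reactions, permanently discontinue all study treatment" | Does not name SJS/TEN, which has its own row |
| 5.1.5.4, opening text | Directs interruption at the drug judged the main cause; Table 3 does not displace clinical judgment | Depends on attribution, case by case |
| 4.6.2 | Requires a stop if the investigator or Sponsor judges continued treatment a danger | Needs that judgment to be made |
| 5.1.5.1 | Stops run-in treatment if a toxicity has not improved in 28 days | Does not cover a case that improves; the Medical Monitor may approve resumption |
| Appendix 10 | Sends dermatologic events back to 5.1.5.4 | Adds no rule |

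Elsewhere Table 3 does order a permanent vemurafenib stop for named events: retinal vein occlusion, and QTcF above 500 ms with a rise of at least 60 ms from baseline. A line of that kind for SJS/TEN would fit the table's existing style. No visible text orders a permanent vemurafenib stop for confirmed SJS/TEN below Grade 4.

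**The case against.** The routing is an inference. The row points to whichever guidelines apply, and nothing says that a specialist-confirmed SJS/TEN case counts as an ordinary rash for the resumption rule. This stands as a limit: the concern is conditional on that reading. It is still the reading the row invites, since it points upward and Grade 3 offers only two branches.

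A rule that stops everything may already apply. Section 5.1.3 groups hypersensitivity and severe cutaneous reactions as one vemurafenib risk, and Section 5.1.3.7 says: "Severe hypersensitivity reactions included generalized rash and erythema or hypotension". An investigator could fairly classify SJS/TEN there and stop all drugs. However, the same section describes SJS/TEN separately as severe dermatologic reactions, and the dedicated row leads to the dermatologic rows. The text is ambiguous, which is a reason to settle it in the row.

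Table 3 is guidance, and Section 4.6.2 compels a stop once a danger is recognized. This also stands: the resumption line is no order to rechallenge, and many investigators would stop vemurafenib anyway. The amendment would write that expected practice down.

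The fix fixes the outcome whatever the attribution, against the principle of acting on the drug judged the main cause. That is a real clinical trade-off, and the sponsor's safety group should own it.

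Two stronger readings are tempting but unsupported. One is that the row removes no active drug in Arm A, which receives atezolizumab placebo, or in the run-in, when nobody receives atezolizumab. The graded guidance the row brings in withholds vemurafenib at once for a Grade 3 non-acneiform case, in both arms and in the run-in. The other is that Section 4.6.1 would let a run-in patient who can no longer receive atezolizumab go on with vemurafenib 960 mg BID. On the Grade 3 path the dose has been reduced, and Section 5.1.5.1 bars escalation after a run-in reduction.

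**Conclusion.** The gap is real but narrow. Table 3 does not say that confirmed SJS/TEN ends vemurafenib, and on a natural reading a Grade 3 case that improves within 28 days goes back on it at a lower dose. The conclusion assumes that the case is graded 3, that it is handled under the non-acneiform branch, and that no one applies the hypersensitivity, main-cause or safety-jeopardy provisions instead. Section 5.1.4, on combination risks, is redacted and could hold relevant text, and the Vemurafenib Investigator's Brochure was not available.

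The number of patients affected cannot be estimated, because the documents give neither an incidence nor a grade split for SJS/TEN. It is probably small. Counting everyone who is not receiving active atezolizumab would not measure it, and the size of a one-level dose reduction would not measure harm. This is a cheap patient-safety improvement of low to moderate severity. It does not affect the efficacy analysis.

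**What to change.** Add to the SJS/TEN row: withhold all vemurafenib/placebo tablets (both bottles, where both are in use) for suspected SJS/TEN; discontinue them permanently if the diagnosis is confirmed, at any grade and including the run-in; this overrides the Grade 1 to 3 dermatologic rows. Leave the Grade 4 row as it is. The sponsor's safety group should decide the cobimetinib action and state it in the same row, since Section 5.1.2 does not list SJS/TEN for cobimetinib. A sentence in Section 5.1.5.1 should say how a patient stopped in the run-in is handled.

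The cost is a wording amendment and a letter to sites, with no new procedures. Stopping every tablet looks the same in both arms, so the blind is kept. The downside is that a rare patient loses the chance of vemurafenib rechallenge. One stopped in the run-in could not enter Cycle 1, because Section 5.1.5.1 requires both oral drugs to be ongoing at that point. Such patients remain in the intent-to-treat population.
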